9.3. Populations for Analyses

The following populations are defined in [Table 9-1](#).

Table 9-1: Study Populations

Population	Description
Intent-to-treat (ITT) analysis population	All randomised participants who received challenge virus and at least 1 dose of IMP
Intent-to-treat infected (ITT-I) analysis population	All randomised participants who received challenge virus and at least 1 dose of IMP, and meet the criterion for laboratory-confirmed RSV infection
Intent-to-treat infected analysis population A (ITT-A)	All randomised participants who received challenge virus and at least 1 dose of IMP and meet the criterion for laboratory-confirmed RSV infection using only assessments prior to taking IMP
Intent-to-treat infected analysis population B (ITT-B)	All randomised participants who received challenge virus and at least 1 dose of IMP and meet the criterion for laboratory-confirmed RSV infection using only assessments after taking IMP
Per protocol (PP) analysis population	All ITT-I analysis population participants who have no major protocol deviations, and who completed the quarantine period up to the final day of quarantine (Day 12) and received all 10 doses of IMP

Population	Description
Safety analysis population	All randomised participants who received challenge virus and at least 1 dose of IMP
PK analysis population	All ITT analysis population participants with at least one post-dose PK result

Membership of participants in each analysis set will be determined at a planned blinded data review meeting, prior to any analysis and database lock.

The primary efficacy analysis population will be on the ITT-I analysis population, and the ITT-A, ITT-B, and PP analysis populations will be used for sensitivity analysis, as defined in the statistical analysis plan (SAP). The safety evaluation will be performed on the safety analysis population. Additional analysis sets may be defined in the SAP.

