9.2. Intent-to-Treat Infected (ITT-I) Population

The intent-to-treat infected (ITT-I) population will consist of all randomised participants who received challenge virus and at least 1 dose of IMP, and meet the criterion for RSV infection. Participants will be analysed in the treatment group they were randomised to.

As per Section 10.7.2 in the protocol, a laboratory-confirmed RSV infection requires one or both of the following definitions to be met:

- At least 2 positive detections by viral load qRT-PCR assay specific for the challenge virus, reported on 2 consecutive days;
- One positive detection by viral load qRT-PCR assay, specific for the challenge virus, in which an aliquot of the same sample has also tested positive in a viral culture assay appropriate for detecting the challenge virus.

For qRT-PCR and the viral culture assay a positive detection is any positive numeric or “detected” value.

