9.3. Intent-to-Treat Infected Analysis Population A (ITT-A) Population

The intent-to-treat infected analysis population A (ITT-A) population will consist of all randomised participants who received challenge virus and at least 1 dose of IMP, and meet the criterion for laboratory-confirmed RSV infection as defined for the ITT-I, using only assessments prior to taking IMP. Participants will be analysed in the treatment group they were randomised to.

The assessments prior to taking IMP includes all qRT-PCR assessments performed before dosing, including the assessment immediately before dosing. In addition, if the infection was seen (via a positive qRT-PCR value) before dosing but the confirmatory value (as per the first part of the viral shedding definition in Section 10.7.2 of the protocol) was taken after dosing, then the participant will be declared as infected before IMP administration, and hence will form part of the ITT-A Population.

Note: The assessments prior to dosing with IMP will include all qRT-PCR and viral culture assessments performed on samples collected before dosing, including the sample collected immediately prior to dosing.

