10. PLANNED STATISTICAL METHODS

10.1. Statistical Considerations

10.1.1. General Definitions

In all applicable summary/analysis presentations of safety endpoints, Baseline is defined as the last non-missing assessment value for a participant, for that particular parameter, that is prior to inoculation of challenge virus, unless over-ruled after review of data at the BDRM or otherwise stated in the appropriate endpoint sections below, whatever the reason for that assessment (e.g. if it is a repeat assessment, then it should be used as the baseline). For efficacy endpoints, the baseline definition is as per the appropriate endpoint sections below. For the derivation of most efficacy endpoints, the first assessment to be used should be the assessment that was taken at the time of first administration of IMP. For example, if a participant was first dosed on the morning of Day 3 then the first qRT-PCR value to be used in the AUC of qRT-PCR viral load (from time of first administration) derivation should be the Day 3 morning assessment. For endpoints using symptom diary card data, the definition of baseline will be defined in greater detail within the appropriate sections of the SAP.

A participant will be classed as infected, and therefore randomised to be dosed, when they have a positive result for RSV-A Memphis 37b by qualitative integrative cycler polymerase chain reaction (qicPCR) from nasal wash sample. IMP administration will be initiated 12 hours after a positive result. However, if a participant remains uninfected, IMP administration will begin on the evening of Day 5.

For participants that extend their time in quarantine beyond Day 12, the additional assessments beyond Day 12 will be listed only, and will not be used for the derivation of any efficacy endpoints. For the avoidance of doubt, the assessment performed on the morning of Day 12 will be the final assessment used for all analyses and summaries for all participants. If additional assessments are taken on Day 12, then they will be listed only. However, the use of data beyond the morning of Day 12 will be discussed at the BDRM.

A participant will be considered to have completed the study after their attendance at the last planned study visit (Day 28 (\pm 3 days)), or the last unscheduled visit (if any occur), as applicable.

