10.7. Statistical Analysis

All efficacy analyses will be based on the ITT-I population as the primary analysis. Where the populations differ to ITT-I population by 1 participant within a treatment group, the primary and selected secondary analyses will be repeated for the ITT-A, ITT-B, ITT and PP populations. This will be reviewed and documented at the BDRM.

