13.2. List of Tables

For the primary endpoint and selected secondary CCI [REDACTED] tables will be repeated for the ITT-A, ITT-B, ITT and PP Populations where the difference between the ITT-I is greater than 1 participant within a treatment group. Where tables are to be repeated on any additional populations, an X has been marked in the relevant column. If a table is repeated, the original table number as produced for the ITT-I population will have .1 added and this final digit will be increased by 1 for repeats on the ITT-A. Similarly, for repeats on ITT-B the number will increase by 2, for repeats on ITT the number will increase by 3 and for repeats on the PP the number will increase by 4. For example, table 14.2.1.1 will be produced for the ITT-I population and will be repeated as 14.2.1.2, 14.2.1.3, 14.2.1.4 and 14.2.1.5 for the ITT-A, ITT-B, ITT and PP populations respectively. If no repeats of a table are required then the original table will not require the final .1.

Table Number	Table Title	Repeated for			
		ITT-A	ITT-B	ITT	PP
14.1.1	Participant Disposition – All Participants				
14.1.2	Demography – Safety Population				
14.1.3	IMP Exposure and Compliance – Safety Population				
14.1.4	Concomitant Medications – Safety Population				
14.2.1.1	AUC of RSV Challenge Virus Viral Load by qRT-PCR from Initial Administration of IMP to Quarantine Discharge – ITT-I Population	X		X	X
14.2.1.2	AUC of RSV Challenge Virus Viral Load by qRT-PCR from Initial Administration of IMP for 6.5 Days – ITT-I Population		X		
14.2.1.3	AUC of RSV Challenge Virus Viral Load by qRT-PCR from Day 2 to Day 12 – ITT-I Population			X	
14.2.1.4	AUC of RSV Challenge Virus Viral Load by qRT-PCR from Initial Administration of IMP to Quarantine Discharge (Untransformed Data) – ITT-I Population		X		
14.2.2.1	Peak Viral Load of RSV Challenge Virus by qRT-PCR from Initial Administration of IMP to Quarantine Discharge – ITT-I Population		X		
14.2.2.2	Time to First Confirmed Undetectable Assessment of RSV Challenge Virus by qRT-PCR from Initial Administration of IMP – ITT-I Population		X		
14.2.2.3	Time to First Confirmed Undetectable Assessment of RSV Challenge Virus after Peak Measure by qRT-PCR following Initial Administration of IMP – ITT-I Population		X		
14.2.2.4	Time to Peak RSV Challenge Virus by qRT-PCR following Initial Administration of IMP – ITT-I Population		X		

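### SAP 9.3 lets samples taken after dosing decide who is in ITT-A, as they already can for ITT-I, so no infected set is fixed before treatment and a fast antiviral effect could be understated

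*SAP*

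**What the plan says.** - **Primary set.** SAP 10.7: "All efficacy analyses will be based on the ITT-I population as the primary analysis".
- **ITT-I infection rule (SAP 9.2).** Either of two routes is enough. The first is "At least 2 positive detections by viral load qRT-PCR assay specific for the challenge virus, reported on 2 consecutive days". The second is one qRT-PCR positive "in which an aliquot of the same sample has also tested positive in a viral culture assay". Any numeric or detected value counts as positive. Neither route is limited to samples taken before dosing.
- **ITT-A.** Protocol 9.3 (Table 9-1) takes participants who "meet the criterion for laboratory-confirmed RSV infection using only assessments" made before IMP. SAP 9.3 repeats this: "meet the criterion for laboratory-confirmed RSV infection as defined for the ITT-I, using only assessments prior to taking IMP". It then adds that a participant who is positive before dosing also belongs to ITT-A if "the confirmatory value (as per the first part of the viral shedding definition in Section 10.7.2 of the protocol) was taken after dosing".
- **Stated reason.** SAP 11, item 1 presents this as clarity, so that ITT-A and ITT-B are mutually exclusive and participants positive on both sides of dosing are placed.
- **Shells.** In SAP 14, the footnotes to the disposition table and the populations listing still call ITT-A a pre-dose set that rests on pre-dose assessments alone.
- **Trigger.** SAP 10.1.1: "A participant will be classed as infected, and therefore randomised to be dosed, when they have a positive result for RSV-A Memphis 37b" by qicPCR. Dosing follows about 12 hours later, or on Day 5 evening if there is no positive result.
- **Repeats.** SAP 10.7 repeats the primary analysis on ITT-A, ITT-B, ITT and PP where a set differs from ITT-I by 1 participant in an arm. SAP 13.2 says "where the difference between the ITT-I is greater than 1 participant within a treatment group".

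**The concern.** Membership of an analysis set should not depend on what the treatment does. Here a participant can be randomised and dosed on a single positive result, and a sample taken on drug may then decide whether that participant counts as infected. RV299 is meant to stop replication. A participant who becomes undetectable quickly on RV299 may never supply the confirming sample, while the same participant on placebo would. Because a Not Detected result enters the AUC as 0 (SAP Appendix 15.1), those removed are the best responders.

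ITT-A as the protocol defined it was the check on this, since it closed before dosing. The SAP's added sentence brings the same dependence into that check. ITT-B is defined on post-dose samples and PP is a subset of ITT-I, so no infected set remains that is settled before treatment starts. The clinical study report would nevertheless footnote ITT-A as pre-dose only. At stake is a proof-of-concept result that could understate a working drug.

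**Working it through.** The documents show no effect size, SD or power, because the section between protocol 9.1 and 9.3 is blacked out. There is no planned figure to reproduce, and that is not counted against the plan.

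**Step 1: who can be confirmed before dosing.** Washes are taken twice daily from Day 2, and the wash immediately before dosing counts as pre-dose.
- *PM trigger:* dosing is the next morning. The PM wash and the next AM wash fall on two consecutive days, so if both are positive the participant is confirmed before dosing.
- *AM trigger:* dosing is that evening. If earlier washes were negative, the positive pre-dose washes share one calendar day. Unless one is culture positive, a wash taken on treatment decides.
- *No trigger, dosed Day 5 evening:* ITT-I membership may rest mainly on post-dose samples.

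**Step 2: direction and scale by algebra.** Let m1 be the true RV299 mean AUC among those who would qualify on placebo, f the fraction lost, and a0 the mean AUC of those lost. The retained mean is (m1 − f·a0)/(1 − f). Illustrative assumptions: placebo mean 100, SD 45, 30 per arm, m1 = 70 (true difference 30), a0 = 8.
- f = 0.05: (70 − 0.4)/0.95 = 73.3, so the difference is 26.7. Power falls from 0.73 to 0.62.
- f = 0.10: (70 − 0.8)/0.90 = 76.9, so the difference is 23.1. Power falls to 0.49.

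Protocol 2.3 expects 65% to 85% infected, which is 40 × 0.65 = 26 to 40 × 0.85 = 34 per arm. A loss of 5% to 10% is therefore about 1 to 3 people (26 × 0.05 = 1.3; 34 × 0.10 = 3.4).

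**Step 3: simulation of the SAP rules.** It used 40,000 to 60,000 participants per arm, the Day 2 to 5 trigger, twice-daily washes and the trapezoidal log10 AUC. Assumed, not taken from the documents: the viral kinetics, 75% infected, a culture threshold of 3.0 to 4.5 log10, and the drug effect. The true difference is among those who would be in ITT-I on placebo (h·log10 copies/mL). Shrinkage is shown as unadjusted / ANCOVA.

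| Assumed response | Lost from RV299 ITT-I | True difference | ITT-I difference (unadjusted) | ITT-I shrinkage | ITT-A shrinkage | ITT difference |
|---|---|---|---|---|---|---|
| All respond, middle strength | 18.1% | 481.2 | 473.0 | 1.7% / 1.0% | 1.5% / 1.1% | 348.6 |
| 50% respond, weakest | 3.3% | 218.1 | 207.8 | 4.7% / 4.5% | 3.2% / 3.0% | 157.7 |
| 50% respond, strongest | 20.1% | 252.1 | 186.2 | 26.1% / 26.2% | 25.0% / 25.0% | 182.3 |
| 20% respond, strongest | 8.1% | 101.4 | 65.1 | 35.8% / 35.7% | 34.4% / 34.3% | 73.3 |

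Across all settings with similar responses, ITT-I shrinks about 1–2% unadjusted and 0.4–1% by ANCOVA, even when many participants are lost, because those kept have low AUCs too. With mixed response ITT-I shrinks 5–36% and ITT-A 3–34%, and baseline adjustment hardly helps. In the third row, power falls from 0.90 to 0.62 at about 29 infected per arm.

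**Step 4: after the fix.** When membership uses only samples up to the pre-dose wash, the arms keep equal shares. With any pre-dose positive this is 72.6% v 72.6%. With full pre-dose confirmation it is 39.6% v 39.6% (about 31% v 31% at the higher culture threshold).

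**The case against.** **The exposed group is limited.** This stands. A culture-positive pre-dose wash confirms infection without any later sample, and a PM trigger followed by a positive pre-dose wash does the same. In the mixed-response simulations about 42% of would-be ITT-I participants were already confirmed and could not be lost. Because any detected value counts, an exposed participant drops out only by becoming fully undetectable before either route is met.

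**ITT does not depend on post-dose virology.** This stands too. ITT takes everyone randomised, challenged and dosed, and is a planned repeat. A reader might infer that the plan contains no comparison free of this selection, and the ITT repeat shows otherwise. It is only a partial safeguard, because an expected 15–35% of it is uninfected, and it is itself conditional on the count rule.

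**The SAP had a reason.** Under a strict pre-dose rule, a participant with one positive on each side of dosing could be in ITT-I but in neither subset. That is a fair reason to say where such participants go. It does not require the post-dose result to decide, since the pre-dose positive alone could place them.

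**Counts by arm are already tabulated.** An imbalance in ITT-I would show in the disposition table. That table would not show how many participants with a pre-dose positive failed confirmation.

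**Skipping ITT-A when it nearly equals ITT-I loses little.** This is true while ITT-A is a subset of ITT-I. If ITT-A takes any pre-dose positive, it is no longer a subset, and similar counts could hide different members.

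**Conclusion.** The contradiction is in the text. SAP 9.3 conflicts with its own pre-dose limit, with protocol 9.3 and with the SAP 14 footnotes, and membership of both ITT-I and ITT-A can turn on samples taken on treatment. Those affected are mainly AM-triggered participants with no culture-positive pre-dose wash. For ITT-I they also include some dosed by default on Day 5 evening.

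If RV299 only removes positives, the bias runs toward no effect. Its size depends on assumptions that the documents do not settle: nil if nobody clears before confirmation, about 1% with similar responses, and up to about one third if only some participants respond strongly.

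Three stronger readings are tempting and not supported:
- *Fast clearers as a class drop out and the effect is sure to shrink.* Many are confirmed before dosing, and nothing in the documents shows clearance before a confirming sample.
- *A positive result would be unsafe.* With no drug effect, membership does not depend on arm, so type I error is not inflated.
- *ITT-I must be replaced as primary.* That is a trade-off between set size, confirmation of infection and selection, and the documents do not decide it.

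This is a low-cost improvement to a sensitivity analysis.

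**What to change.** Before unblinding:

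1. In SAP 9.3, delete the sentence beginning *In addition*, so that ITT-A uses pre-dose samples only. There are two workable definitions. One restores the protocol's laboratory confirmation from pre-dose samples. The other takes any positive pre-dose qRT-PCR, which keeps more participants and still places those positive on both sides of dosing. Keep ITT-B defined as those not in ITT-A, and make the SAP 14 footnotes match.
2. Run ITT-A unconditionally for the primary endpoint, as a sensitivity analysis reported beside ITT-I, which stays primary. Reconcile the repeat thresholds in SAP 10.7 and 13.2 for the other sets.
3. Tabulate by arm the participants with a pre-dose positive who fail ITT-I.

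The cost is SAP wording and one always-run analysis with its table. Full pre-dose confirmation gives a smaller ITT-A. Any pre-dose positive keeps some single unconfirmed positives, which dilute the set equally in both arms. Neither definition recovers participants who are negative before dosing and whose infection RV299 then blocks. For them the ITT repeat remains the reference.

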9.4. Intent-to-Treat Infected Analysis Population B (ITT-B) Population

The intent-to-treat infected analysis population B (ITT-B) population will consist of all randomised participants not already in the ITT-A Population, who received challenge virus and at least 1 dose of IMP, and meet the criterion for laboratory-confirmed RSV infection as defined for the ITT-I, using only assessments after taking IMP. Participants will be analysed in the treatment group they were randomised to.

Note: The assessments after dosing with IMP will include all qRT-PCR and viral culture assessments on samples that are collected after dosing and will not include the sample collected immediately prior to dosing.

9.5. Per Protocol (PP) Population

The per-protocol (PP) population will consist of all ITT-I population participants who have no major protocol deviations, and who completed the quarantine period up to the final day of quarantine (Day 12) and received all 10 doses of IMP. Participants will be analysed in the treatment group they were randomised to.

9.6. Safety Population

The safety population will consist of all randomised participants who received challenge virus and at least 1 dose of IMP. Participants will be analysed according to the treatment they received.

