
 To evaluate the safety of multiple orally administered doses of RV299 when compared to placebo. 	
 Safety data including, but not limited to, occurrence of AEs from initial administration of IMP up to the Day 28 follow-up. Occurrence of SAEs from initial administration of IMP up to the Day 28 follow-up.

 To monitor the safety of the challenge virus. 	
 Occurrence of AEs related to the viral challenge from viral challenge (Day 0) up to the Day 28 follow-up. Occurrence of SAEs related to the viral challenge from viral challenge (Day 0) up to the Day 28 follow-up. Use of concomitant medications from viral challenge (Day 0) up to the Day 28 follow-up.

Objectives	Endpoints

Pharmacokinetics
	

 • To characterise the PK profile of RV299 after a single oral dose and after multiple oral doses in plasma from healthy participants inoculated with RSV. 	
Secondary endpoints related to PK include, but are not limited to:
 
 • Time to maximum plasma concentration (t_{max}), terminal half-life ($t_{1/2}$), C_{max}, area under the plasma concentration-time curve from time zero to the end of the dosing interval (AUC_{τ}), AUC_{0-24h}, and area under the plasma concentration-time curve from time zero to infinity ($AUC_{0-\infty}$).

CCI
 	
	
	
	
	
	
	
	
	
	
	
	
	
	
	
	
	
	
	
	
	
	
	
	
	
	
	
	
	
	
	
	
	
	
	
	
	
	
	
	
	
	
	
	
	
	
	
	
	
	
	
	
	
	
	
	
	
	
	
	
	
	
	
	
	
	
	
	
	
[figure not shown] Females of childbearing potential must have a negative pregnancy test prior to enrolment. Females of non-childbearing potential: 
 Post-menopausal females defined as amenorrhea for ≥ 12 months with no alternative medical cause. A high follicle-stimulating hormone (FSH) level, within appropriate post-menopausal range, may be used to confirm post-menopausal state in the absence of combined hormonal contraception or hormone replacement therapy. If there is < 12 months of amenorrhea 2 FSH samples are required at least 4 to 6 weeks apart. Documented status as being surgically sterile (e.g., tubal ligation, hysterectomy, bilateral salpingectomy, and bilateral oophorectomy).

No.	hVIVO APPROVED STANDARD INCLUSION CRITERIA (Viral Challenge Volunteer Studies) Final v11.0, 08FEB2022

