9.4.7. Safety Analyse(s)

All safety analyses will be computed on the safety analysis set.

Unless otherwise stated, safety endpoints will be presented in terms of descriptive statistics only.

Adverse events will be coded using the most current version of the Medical Dictionary for Regulatory Activities and summarised descriptively by system organ class, preferred term, and study intervention arm for the number of AEs reported and the number and percentage of participants reporting each AE.

A by-participant AE data listing including onset and resolution dates, verbatim term, preferred term, treatment, severity, relationship to treatment, action taken, and outcome will be provided.

Other safety endpoints that will be presented by study intervention arm include laboratory evaluations (biochemistry, haematology, cardiac enzymes, and urinalysis), vital signs assessments, physical examinations, 12-lead ECG, and spirometry. Additionally, physical examinations will be listed.

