6. STUDY DESIGN

6.1. Summary of Study Design

This is a single-centre, randomised, double-blind, placebo-controlled, proof-of-concept study in healthy adult male and female participants from 18 to 55 years of age, inclusive. The primary goal of this Phase 1b study is to assess the antiviral activity of RV299 against RSV in the viral challenge model. In addition, the safety, tolerability, and PK of RV299 will be assessed.

A total of 80 participants is planned to be enrolled in this study: 40 participants on RV299 and 40 participants on placebo.

The study is divided into the following study phases:

- Screening phase: from Day -90 to Day-3 pre-human viral challenge (HVC). Historical generic screening data collected through the hVIVO generic screening process may be transferred to this study after the study-specific consent form has been signed by the participant.
- Inpatient phase: Participants will be resident in the quarantine unit for approximately 15 days (from Day -2 to Day 12). Procedures will include:
 - Pre-HVC:
 - Admission to quarantine unit on Day -2/-1.
 - Baseline assessments will be conducted as per Schedule of Events (SoE) up to Day 0, pre-challenge.
 - HVC: RSV-A Memphis 37b virus inoculation on Day 0.
 - Post-HVC:
 - Randomisation to receive RV299 or matched placebo.
 - Administration of IMP (RV299/placebo). Each participant will receive IMP twice daily (~12 hours interval) for 5 consecutive days:
 - IMP dosing to start on confirmation of RSV infection, i.e., after a positive result by qualitative integrative cycler polymerase chain reaction (qicPCR). The qicPCR of nasal wash will be performed twice daily on Days 2-5 (Day 5 morning only), or until a positive result is received, whichever is sooner. The earliest start of IMP dosing will be in the evening of Day 2 post-HVC (IMP will be initiated 12 hours \pm 1-hour post nasal wash confirmation of infection)
 - OR
 - IMP would start in the evening of Day 5, if no positive result obtained by qicPCR
 - Day 1 onwards and each day study assessments will be conducted as per SoE.
 - Participants will be discharged from the quarantine unit on Day 12 (or may remain longer at the discretion of the principal investigator [PI]/investigator).
- Outpatient phase:
 - Final visit: Day 28 (\pm 3 days).

The overall study design is depicted in

Table 1.

Table 1: Study Schematic: On-study Participant Progression

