10.9. Safety Analysis

All analyses of safety endpoints will be descriptive only. The safety population will be used for all safety presentations.

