10.9.1. Adverse Events

All adverse events (AE) will be coded using MedDRA, Version 25.0.

An adverse event is defined as treatment emergent if the onset date is on or after the date of first dosing with IMP. Should any onset date for an adverse event be missing or only a partial date recorded (such that it cannot be determined if the event onset was prior to start of IMP or not) then it will be assumed that the event is treatment emergent, unless the adverse event stop date indicates otherwise.

Similarly, an AE is defined as challenge emergent if the onset date is on or after the date of inoculation. Should any onset date for an adverse event be missing or only a partial date recorded (such that it cannot be determined if the event onset was prior to inoculation or not) then it will be assumed that the event is challenge emergent, unless the adverse event stop date indicates otherwise.

An AE can be both challenge emergent and treatment emergent. Any AE with an onset date earlier than the inoculation date will be classified as a pre-treatment AE.

If a participant experiences more than one adverse event with the same preferred term, that preferred term will be counted only once. It will be assigned the greatest observed severity and the strongest relationship to IMP among those events for the tables in which those characteristics are summarised.

Pre-treatment AEs will be identified in a patient listing.

A summary of treatment-emergent AEs will be presented by treatment group showing the number of events, number of participants with events (also split by severity; mild, moderate, severe), number of participants with SAEs, number of participants with related events, number of participants with events

leading to early withdrawal from the study and the number of participants with events leading to early discontinuation of IMP.

Further summaries will present the treatment-emergent AEs by:

- Treatment group, SOC and PT.
- Treatment group, SOC, PT and severity.
- Treatment group, SOC, PT and relationship to IMP.

Further summaries will present the challenge-emergent AEs by:

- Treatment group, SOC, PT and relationship to challenge agent.

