14.2.3.7	Time to Symptom Resolution by 10-Item Diary Card from Initial Administration of IMP to 24-Hours Symptom Free - ITT-I Population	X			
14.2.3.8	Time to Symptom Resolution by 10-Item Diary Card from Peak Total Symptom Score to 24-Hours Symptom Free - ITT-I Population	X			

Table Number	Table Title	Repeated for ITT- A ITT- B ITT PP
14.2.3.9	Time to Peak Symptom Score by 10-Item Diary Card from Initial Administration of IMP - ITT-I Population	X
14.2.4.1	Total Weight of Mucus Produced from Initial Administration of IMP to Quarantine Discharge by Assessment - ITT-I Population	X
14.2.4.2	Total Number of Tissues Used from Initial Administration of IMP to Quarantine Discharge by Assessment - ITT-I Population	
CCI	[REDACTED]	
	[REDACTED]	
14.3.1.1	Overall Summary of Treatment Emergent Adverse Events – Safety Population	
14.3.1.2	Treatment Emergent Adverse Events by System Organ Class and Preferred Term – Safety Population	
14.3.1.3	Treatment Emergent Adverse Events by System Organ Class, Preferred Term and Severity – Safety Population	
14.3.1.4	Treatment Emergent Adverse Events Related to RV299 by System Organ Class and Preferred Term – Safety Population	
14.3.1.5	Adverse Events Related to Challenge Agent by System Organ Class and Preferred Term – Safety Population	
14.3.2	Haematology Parameters: Summary – Safety Population	
14.3.3	Biochemistry Parameters: Summary – Safety Population	
14.3.4	Coagulation Parameters: Summary – Safety Population	
14.3.5	Cardiac Enzymes Parameters: Summary – Safety Population	
14.3.6	Urinalysis Parameters: Summary – Safety Population	
14.3.7	Vital Signs Parameters: Summary – Safety Population	
14.3.8	Spirometry Parameters: Summary – Safety Population	
14.3.9	12-Lead Electrocardiogram Parameters: Summary – Safety Population	

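### Challenge-virus safety is counted from inoculation but tabulated only in participants who went on to receive IMP, and challenge-related serious events have no table

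*SAP*

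**What the plan says.** Protocol Section 3 lists monitoring of challenge-virus safety as a secondary objective, separate from the safety of RV299. Its first endpoint is "Occurrence of AEs related to the viral challenge from viral challenge (Day 0) up to the Day 28 follow-up". Two more cover the same period: challenge-related serious adverse events and concomitant medication. SAP Section 7.2 repeats all three.

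SAP Section 10.9.1 is consistent with that window: "Similarly, an AE is defined as challenge emergent if the onset date is on or after the date of inoculation".

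The analysis set is narrower. SAP Section 9.6 states: "The safety population will consist of all randomised participants who received challenge virus and at least 1 dose of IMP". Protocol Table 9-1 has the same definition. SAP Section 10.9 adds "The safety population will be used for all safety presentations", and Protocol Section 9.4.7 says "All safety analyses will be computed on the safety analysis set". The one table of challenge-related events, 14.3.1.5 in SAP Section 13.2, is titled "Adverse Events Related to Challenge Agent by System Organ Class and Preferred Term – Safety Population".

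Randomisation and dosing come after inoculation. SAP Section 6.1 says "The earliest start of IMP dosing will be in the evening of Day 2 post-HVC". The latest start is the evening of Day 5, for participants with no positive qicPCR.

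**The concern.** The endpoint describes everyone who was given the virus. The table describes those who were given the virus, then randomised, then dosed. Someone who leaves in between is removed from the table, and a challenge-related event is one possible reason for leaving. Protocol Section 7.2, for example, names clinically significant laboratory findings and intercurrent illness among the grounds for ending study-drug receipt. Where that happens before the first dose, exclusion depends on the outcome being counted, and the tabulated incidence is biased for the stated objective.

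A second gap concerns seriousness. Challenge-related serious events are a named endpoint, yet no table in SAP Section 13.2 summarises them.

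**Working it through.** The plan gives no figure to reproduce, so the check sets the definitions side by side and then illustrates the size.

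**1. Who is missing.** The endpoint population is all inoculated participants. The safety population is those inoculated, randomised and dosed. Dosed participants have been randomised, so the difference is exactly the inoculated who were never dosed, whether randomised or not. The window in which someone can fall into that group opens on Day 0 and closes at first dose, between the evening of Day 2 and the evening of Day 5. No all-inoculated set appears in SAP Section 9 or in the visible list of safety tables, although Protocol Section 9.3 allowed the SAP to add sets.

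**2. Serious events.** The shell for Table 14.3.1.5 reuses the layout of 14.3.1.4: system organ class, preferred term and relationship, with no seriousness field. The only row for serious events is in the overall adverse event summary, Table 14.3.1.1, which is limited to onset on or after the start of IMP. A challenge-related serious event before IMP is therefore not summarised as serious, even in a participant who is later dosed.

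**3. Medication from Day 0.** SAP Section 10.5 summarises concomitant medication on the safety population. Medication stopped after inoculation and before IMP starts is classed as prior to IMP, and prior medication is only listed. The third endpoint is therefore incompletely tabulated even in dosed participants.

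**4. Size, for illustration.** Inputs:
- 80 inoculated. SAP Section 6.1 plans 80 enrolled, 40 + 40, and Protocol Appendix 7 defines enrolment as inoculation.
- *d*, the proportion leaving before first dose. The documents give none, so 1% to 5% is assumed.

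Expected number missing = 80 × *d*. Chance that at least one is missing = 1 − (1 − *d*)^80.

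| Assumed *d* | Expected missing | Chance of at least one |
|---|---|---|
| 1% | 0.8 | 0.55 |
| 2% | 1.6 | 0.80 |
| 3% | 2.4 | 0.91 |
| 5% | 4.0 | 0.98 |

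Now suppose that 2 of the 80 leave undosed because of a challenge-related event, so 80 − 2 = 78 are tabulated.
- If 2 dosed participants also have such an event, the table shows 2/78 = 2.6%, against 4/80 = 5.0% of all inoculated.
- If no dosed participant has one, the table shows 0/78 (Clopper-Pearson 95% interval 0 to 1 − 0.025^(1/78) = 4.6%), against 2/80 = 2.5% (0.3% to 8.7%). This is the extreme case.

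The SAP's safety analyses are descriptive, so these intervals only show scale and are not planned outputs.

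**The case against.** The strongest reply is that nothing is lost from the report. SAP Section 10.1.2 puts all collected data in listings. Listing 16.2.7 carries, for each event, a challenge-emergent flag, seriousness and its criteria, outcome, and relationship to the challenge agent. The disposition table covers all participants, has a row for receipt of challenge agent, and gives adverse event as a withdrawal reason. Serious-event reporting and the challenge-virus stopping rule in Protocol Table 7-1 do not depend on the safety population. The SAP also follows the protocol's own set, so it is not a deviation. All of this stands. It answers any charge of concealment, but a listing supplies neither an incidence nor a denominator for a stated endpoint.

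The affected group is also narrow. Participants are inpatients throughout the window. Under Protocol Section 10.3.6.2, diary-card symptoms and pyrexia after inoculation become adverse events only if they meet the definition and are judged clinically significant. The disposition shell does have a withdrawal reason for participants never dosed. It sits apart from the adverse event reason, however, and does not show that the SAP expects challenge-related events to prevent dosing. This too stands and limits the weight of the point.

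A reader might go further and infer that all events between inoculation and first dose are left out of Table 14.3.1.5. The documents do not support that. Challenge-emergent events are dated from inoculation, so pre-IMP events in dosed participants still count; only the never-dosed drop out. A reader might also infer that the table could falsely show that no serious challenge-related event occurred. It displays seriousness for nobody, so the accurate statement is that it omits the undosed participant's event.

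**Conclusion.** The point holds as a reporting gap that should be closed. As written, the plan tabulates challenge-related adverse events in a set entered two to five days after the endpoint starts, and entry can depend on the outcome. It gives challenge-related serious events no table, and it only lists medication stopped between inoculation and first IMP. These conclusions follow from the text and need no assumption about numbers.

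The size is uncertain and probably small. The 0.8 to 4.0 missing participants rest on an assumed 1% to 5% loss among 80 inoculated, and the contrast of 0/78 with 2/80 is an assumed extreme, not a forecast. The comparison of RV299 with placebo is unaffected, because a dosed set suits treatment-emergent events. Redacted parts of the SAP cannot be checked, but the visible safety tables use no other population.

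**What to change.** - Define a challenge-safety set: all participants inoculated with RSV-A Memphis 37b, whether or not randomised or dosed.
- Use it for Table 14.3.1.5, with columns for RV299, placebo, inoculated but not dosed, and overall.
- Add a row for challenge-related serious adverse events with onset from Day 0.
- Summarise medication use from Day 0 on the same set, including medication stopped between inoculation and first IMP.
- Keep the present safety population for the treatment-emergent tables.

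The cost is small: one added set, changed denominators and footnotes, and a column for participants who may have no assigned arm. No new data are needed, because Protocol Section 8.5.1 already collects adverse events from study-specific consent and Section 6.5 does the same for medication.
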